### 1.1 Specific Aims

- A. Compare the effectiveness, safety, and cost of two treatments for moderate to severe FI in 194 male and female patients in a multi-center RCT; the interventions are biofeedback therapy (5 required weekly sessions with the option of an additional 6th visit, as needed) and perianal injection of the inert bulking agent dextranomer (INJ; Solesta). A ≥75% reduction in average weekly FI episodes compared to baseline will define a responder. The primary efficacy analysis will occur 3 months following the start of each treatment, with long-term follow-up through 2 years. Secondary outcomes will include a validated FI severity scale, a disease-specific quality of life scale, and measures of psychological distress.
  - Research objective 1 (primary). For the primary test of efficacy, the null hypothesis is that the proportion of responders in the two treatment groups will not be different. Secondary analyses will test for equivalence at other time points (e.g., 6, 12 and 24 months follow up) and will compare treatment groups on other secondary outcome measures.
  - Research objective 2 (primary). For the primary test of safety, the null hypothesis is that at 3 months follow up, the proportion of patients with adverse events (AEs) of pelvic pain of grade II or higher based on Common Terminology Criteria for AE (CTCAE) criteria, treatment site infection, or SAEs requiring hospitalization will not be different in the BIO or INJ groups. Secondary analyses will evaluate this outcome at 6, 12, 18, and 24 months follow up.
  - Research objective 3 (primary). At 3 months follow up, the estimated average cost for enhanced medical management non-responders will not be different for the two treatments. Secondary analyses will evaluate this outcome at 6, 12, 18, and 24 months.
- B. Compare efficacy in patients who complete all assigned treatment visits. Efficacy may be influenced by the number of BIO treatment sessions and the requirements to learn and practice new skills. Thus, in a secondary analysis, the primary efficacy outcome will be compared between treatment groups in the subset of participants who completed the treatment to which they were randomized.

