  - Research objective 8. To estimate the cost of delivering medical treatment and compare to the cost of delivering any of the other two treatments.
- F. Compare the cost effectiveness of two treatments for moderate to severe FI.
  - Research objective 9: To estimate the average cost effectiveness (i.e., cost per quality adjusted life year gained excluding costs that are only for research purposes) among conservative medical management non-responders for the two treatments at 6, 12, 18 and 24 months.

This 4-site geographically dispersed study will identify the most optimal, durable, safe, and inexpensive treatment for moderate to severe FI patients. In addition, this project will demonstrate the efficacy of enhanced medical management of FI, explore the mechanisms of action for the study treatments, and identify the factors that predict the response to treatment. A successful outcome may result in changes to management strategies.

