2.2.2. Perianal INJ of Dextranomer Bulking Agent: Two systematic reviews published in 2010 concluded that there was no evidence for the efficacy of injectable bulking agents for the treatment of FI, but another review which incorporated uncontrolled studies concluded that 56% of patients were treatment responders including 13% who achieved continence. Subsequent to these publications, Graf and colleagues reported a multisite RCT of the effects of dextranomer INJ versus sham (saline) injections in 206 patients. At six months follow-up, 53% of the dextranomer-INJ patients had at least a 50% decrease in FI compared to 21% of sham injected patients. At 12 months, the responder rate was sustained with 45% of the dextranomer INJ group achieving at least a 50% decrease in FI relative to baseline. Based on this multicenter RCT, dextranomer was approved by the FDA for treatment of FI.

In the only other controlled study, INJ were compared to BIO. The 62 patients in the BIO group were instructed to practice at home 5 days per week for 6 months with a commercially available device that could also provide electrical stimulation, and half of the patients used electrical stimulation as an adjunctive

treatment. Patients were supervised by a physical therapist five to six times during this period. However, this report provided few details on how BIO training was done. The treatment protocol for INJ was similar to that used by Graf. Results showed that FI improved in both treatment groups (St. Mark's FI severity scores decreased from 12.9 to 8.3 in the INJ group and from 12.6 to 7.2 in the BIO group), but there were no differences between treatments.

In the Graf multisite study, anorectal physiology was not evaluated. In the controlled trial comparing BIO with INJ, the dextranomer INJ did not increase anal resting or squeeze pressure. Hence the mechanism by which dextranomer improves fecal continence is unknown.

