### 3.0 Study design:

The overall study design, shown in Figure 1, is an unmasked, multisite, randomized, parallel group study comparing the effectiveness of two treatments for moderate to severe FI. This study design builds on the core recommendations of the NIDDK Workshop for design of an ideal comparative effectiveness RCT. It is a parallel group design which has the following features:

- 1. *Baseline:* Patients will keep a daily symptom diary for two weeks prior to the Baseline visit to (a) document that they meet the minimum frequency required for inclusion in the study and (b) provide a reference value for assessing treatment response at the end of EMM and at 3, 6, 12, and 24 months follow-up points. Adverse events and cost will be reassessed at each in-person visit and at 3-, 6-, 12-, 18- and 24-month follow up assessments.
- 2. Enhanced medical management: All patients meeting inclusion criteria will first be treated with EMM for 4 weeks to identify those who really need a more expensive and more invasive treatment. The key components of treatment are patient education about the basic physiological mechanisms for defecation, diet and medication to normalize stool consistency, and pelvic floor exercises taught by printed instructions. (Section 6.1) Additional goals of the EMM protocol are (a) to ensure that patients randomized to INJ meet the accepted criteria by failing to respond to EMM, and (b) to document the efficacy and the durability of systematically applied, optimized EMM. This design is similar to the one used in the Heymen RCT which provides the strongest evidence for the efficacy of BIO. We believe the exclusion of patients

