#### Table 3: Preliminary Data for Sample Size Calculations

#### Table 4: Preliminary Data on Other Outcome Measures

Outcome Measure	BIO Heymen 	INJ Graf 	Sample size required per group
 Adverse events (% subjects)	0%	9.6%	74
 Estimated cost (\$)	\$1,435	\$7,408	
 % Change in quality of life impact	11.9% (SD = 21.5)	27.3%	32
 St Mark's Score or FISI, Average % decrease	36% (SD = 45.8)	17.9%	102

There were 128 AEs in 136 patients, but some were relatively minor. We list only the estimated rate of pain, fever, and abscess (13 events in 136 patients). Sample size calculations are for tests of proportions with alpha = .05 and beta = .80. Costs are estimated from published Medicare reimbursement tables are not compared statistically.

Continuous outcomes for quality of life and FI severity calculations assume alpha = .05 and beta = .80.

It is anticipated that up to 15% of participants enrolled in the study will drop out (with no further follow up). before completing enhanced medical treatment. If the number who drop out exceeds 15%, additional subject will be recruited and enrolled into the study, but prior research suggests that 15% is a reasonable estimate. Another 15-20% are expected to achieve a 75% reduction in FI during EMM and will need to be replaced Thus,

we anticipate that approximately 285 participants will need to begin EMM treatment in order for 194 to complete the run-in phase and be randomized to BIO or INJ (97 per group). The participant flow diagram is shown in Figure 3.

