## 7.0 Randomization and Masking

#### 7.1 Randomization

Enrollment in the study will be defined as satisfying all eligibility criteria and signing informed consent (see Section 9.4). Randomization to the two interventions being compared BIO and INJ) will not occur until patients have completed EMM and been classified as a non-responder based on showing a less than 75% reduction in the average frequency of solid, liquid, and/or staining FI events compared to the two-week baseline. See Figure 4 for Decision Tree governing patient flow through the study.

Randomization will occur in a ratio of 1:1 with an equal chance of being randomized to each treatment group. Randomization will be performed using randomly permuted blocks, with block sizes known only to the DCC, and will be stratified by clinical site and sex (male and female). For each participant, the web-based electronic data capture system will determine the treatment allocation from a static randomization table. Personnel at the clinical sites will not have access to the randomization table in order to minimize the risk of selection bias.

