Assess the efficacy and durability of enhanced medical treatment and identify patient characteristics that predict treatment response. The proportion of responders will be calculated at the end of EMM and at 3-, 6-, 12-, and 24-month follow-up. A longitudinal generalized linear model will be constructed to predict treatment response based on time and clinical site; the model will account for the lack of independence between multiple measures assessed over time on the same study participant by modeling the within-participant covariance structure. Participants who are non-responders to EMM at 3 months will continue to be classified as non-responders at 6, 12, and 24 months. Participants without a valid bowel diary will be classified as non-responders at that time point, and those who initiate off-study treatment for FI after EMM will be classified as non-responders at each subsequent visit/assessment. Using this model, we will compare response rates at the end of EMM to response rates at 3, 6, 12, and 24 months. We will also calculate 95% confidence intervals for the percentage of participants reporting AEs during EMM. Costs of EMM will be estimated and compared to costs of the other study interventions using methods described for cost of care analysis. The predictors of response to EMM at baseline, 3, 6, 12, and 24 months will be explored using generalized linear modeling.

*Cost- Effectiveness Analysis.* We will estimate the impact of each intervention on quality-adjusted life-years (QALYs). QALYs are summary measures of morbidity and mortality that typically range from 0 to 1 over a full year, where 1 represents perfect health. QALY estimates will be obtained from the EQ-5D; annual QALY measures will be calculated. We will assess the average cost per QALY gained for each intervention and the incremental cost per QALY gained by comparing the interventions ordered from lowest to highest QALY gains (i.e., comparing the intervention with medium effectiveness to the intervention with lowest effectiveness and the intervention with highest effectiveness to the intervention with medium effectiveness).

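### The plan promises to demonstrate the efficacy of enhanced medical management (EMM), but the run-in has no control and can only estimate an uncontrolled response rate and its durability

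*Combined protocol and SAP*

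**What the plan says.** Four places in the combined protocol and SAP attach efficacy to EMM:

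- Section 1.1, closing paragraph: "this project will demonstrate the efficacy of enhanced medical management of FI".
- Section 3.0, item 2, which gives as a goal "to document the efficacy and the durability of systematically applied, optimized EMM".
- Aim E in section 1.1, whose title sets out to assess efficacy and durability.
- Section 8.3, where the paragraph for that aim repeats the same title.

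The design is as follows. Section 3.0, item 2: "All patients meeting inclusion criteria will first be treated with EMM for 4 weeks". Section 7.1 says that randomization "will not occur until patients have completed EMM and been classified as a non-responder". The responder rule is in section 1.1: "A ≥75% reduction in average weekly FI episodes compared to baseline will define a responder". The reference is the two-week baseline diary. Section 5.1 requires that diary to average at least 2 episodes per week for entry, and the Schema allows it to be kept for two further weeks if the investigator thinks the first diary missed the extent of the incontinence.

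The analysis in section 8.3 is: "The proportion of responders will be calculated at the end of EMM and at 3-, 6-, 12-, and 24-month follow-up". A longitudinal model then compares the end of EMM with the later visits. Research objective 6 is worded more modestly, as estimating a responder rate.

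**The concern.** Efficacy is a claim about what EMM adds over the same four weeks without it. With no such group, the before-after rate mixes four things: any effect of EMM, regression to the mean after selection on a high diary count, ordinary fluctuation in a two-week count, and non-specific improvement. Section 3.0 itself says that EMM contains non-specific components. A larger sample narrows the interval around the mixture but does not separate its parts.

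EMM response is a named aim with two years of follow-up, and section 1.1 says a successful outcome may change management. Followed as written, a response near the expected rate could be reported as demonstrated efficacy of EMM.

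**Working it through.** **1. The plan's own figures.** The text after Table 4 says "Another 15-20% are expected to achieve a 75% reduction in FI during EMM". Section 5.4 uses 20%, with 15% attrition, from 285 entering EMM:

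285 × 0.85 × 0.80 = 193.8, which reproduces the 194 randomized.

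(The printed 57 responders is 20% of 285. The route to 194 implies 20% of 242, about 48; with 57, 285 − 43 − 57 = 185. This is a minor mismatch of denominators and does not affect the point.)

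**2. What the planned estimate would give.** Wilson 95% interval, p = 0.20, n = 285, z = 1.96:

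[p + z²/2n ± z√(p(1−p)/n + z²/4n²)] / (1 + z²/n) = (0.2067 ± 0.0469) / 1.0135 = 15.8% to 25.0%.

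With 48/242 it is 15.3% to 25.3%. Either interval is precise, but it describes change from baseline. No value inside or outside it is a no-EMM rate, because section 8.3 names none. The comparisons with 3, 6, 12 and 24 months address durability.

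**3. Response with no EMM effect, by hand.** Entry needs at least 2 × 2 = 4 episodes in the diary. From a count of 4, a 75% reduction means 1 or fewer. Under Poisson variation and no change in the true rate:

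- True rate 2 per week (mean 4 in two weeks): e⁻⁴(1 + 4) = 9.2%.
- True rate 1 per week (mean 2), entering on a high count of 4: e⁻²(1 + 2) = 40.6%.
- True rate 4 per week (mean 8), entering on 8, so that 2 or fewer counts as response: e⁻⁸(1 + 8 + 32) = 1.4%.

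The answer depends on where patients' true rates lie relative to the entry threshold.

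**4. Averaged over patients (simulation).** The documents do not give the distribution of true rates or the within-person diary variability, so both are assumptions. True rates are gamma-distributed with mean 2-5 per week before selection and between-person CV 0.7-1.0. Baseline and follow-up counts are independent given the person's rate, and entry requires a baseline count of 4 or more.

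| Within-person variation | Entry on diary only | Also true rate ≥ 2/week |
|---|---|---|
| Poisson only | 3-9% | 1-4% |
| Extra CV 0.3 | 5-13% | about 4-7% |
| Extra CV 0.5 | about 11-21% | 9-14% |

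The right-hand column stands in for the self-report half of the entry criterion in section 5.1. A second model, with overdispersion as a variance-to-mean ratio and a wider set of rates, gave 2-8% at ratio 1 (Poisson), 5-17% at ratio 2 and 9-24% at ratio 3.

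**5. Check against the documents' one no-treatment figure.** Section 2.2.2 reports that "53% of the dextranomer-INJ patients had at least a 50% decrease in FI compared to 21% of sham injected patients". Settings in these models with about 20% response at the 50% threshold give roughly 4-8% at 75%. The extra CV 0.5 settings (diary-only entry) give 29-42% at 50%, well above the 21%, so the top of the table fits that figure poorly. The match is loose in any case: the sham rate is at six months, after a saline procedure, and may include a placebo response.

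**The case against.** The best case for the plan has four parts.

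- **Purpose.** Section 3.0, item 8 gives the run-in's main purpose as excluding patients who do not need costlier treatment. Objective 6 only estimates a rate, and section 8.3 tests EMM against no null. This is true, and it supports the point: the objective is worded correctly, and the efficacy statements around it are not.
- **Repeated diaries.** A chance responder is unlikely to respond again. In the no-effect model with diary-only entry, response at both the end of EMM and 3 months falls to about 0.4-6%, and adding 6 months gives about 0.1-2.5%. This stands: sustained response filters much of the diary noise. It does not remove lasting non-specific or natural improvement.
- **Evidence the other way.** Section 2.2.3 cites a trial whose medical-management controls did not improve at all, which would put the background rate near zero. The protocol itself doubts the credibility of that control condition, so this widens the uncertainty and does not settle it.
- **Prior experience.** Section 6.1 reports a 60% mean reduction and 22% adequate relief in a previous run-in. That run-in is described with no untreated comparison either.

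A reader might go further and infer that a material part of the 20% would certainly occur without EMM, or that EMM does not work. The documents support neither. They give no 75% response rate without EMM, and the modelled share runs from about 1% to more than 20% on assumption alone.

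**Conclusion.** The claim of efficacy is stronger than the design allows. That conclusion rests on the text alone: universal EMM, randomization only afterwards, a reference diary that is also the entry test, and no comparator or null rate in section 8.3.

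The size of the non-EMM share is not identified. A no-effect count model gives roughly 1-9% against the expected 15-20% with Poisson variation only, and more if patients' diaries vary more than that. These figures depend on the assumed distribution of rates, the assumed within-person variability and how the self-report entry criterion is represented. They show that the share could matter, not that it does.

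A reader might also infer that the main trial is compromised. It is not: both arms pass through the same run-in before randomization, so the BIO versus INJ comparison is unaffected.

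**What to change.** In Aim E and the closing paragraph of section 1.1, section 3.0 item 2, and the matching paragraph of section 8.3, replace efficacy of EMM with *response rate and durability of response during EMM (uncontrolled)*, and drop the word demonstrate. Add one sentence to section 8.3 stating that regression to the mean after selection on the baseline diary, natural fluctuation and non-specific effects cannot be separated from an effect of EMM.

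I would not add a no-change benchmark built from week 1 versus week 2 of the baseline diary. It would miss month-to-month and non-specific change, the two weeks are truncated by the entry rule on their total, and an observed-minus-expected figure would look like an adjusted EMM effect while remaining unidentified.

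The cost is a few wording changes, with no new data and no change to patient procedures or to the randomized analysis. The downside is a less favourable claim about EMM.

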## 2.0 Background and Significance

*2.0.1 Prevalence and epidemiology:* Fecal incontinence (FI) is the involuntary passage of solid or liquid stool. The age-adjusted prevalence of FI occurring in the past month in non-institutionalized U.S. adults is 9% in women and 8% in men, and this increases to 15% in men and women by age 70^1. FI occurs at least weekly in 3% of non-institutionalized adults. Up to one in five women in the community report one or more episodes of FI in the past year. The prevalence of FI is higher in primary care clinics compared to the general population because poor health is a risk factor for FI; an estimated 37% of primary care patients self-report FI on questionnaires, although this is rarely reported to their physician or identified in their medical record.

2.0.2 Impact on quality of life and health care costs: FI has a major impact on quality of life being associated with symptoms of anxiety and depression and with avoidance of leaving home or inviting friends to visit. FI increases the likelihood of admission to a nursing home, and the prevalence in nursing homes is 48%. It is associated with high health care costs for the individual and, partly through its impact on nursing home referral, also with high costs to society.

### 2.1 Rationale for conducting a comparative effectiveness trial

*Evidence-based treatments available for FI:* Several treatment approaches have been described for FI covering a spectrum from self-management with pads through biofeedback (BIO), drugs, injections with bulking agents (INJ), sacral nerve electrical stimulation (SNS), up to surgical reconstruction or implanting an artificial

anal sphincter. At present, three treatments for FI are supported by randomized controlled clinical trials (RCTs) and are frequently employed; they are BIO, INJ of the bulking agent dextranomer, and SNS.

These three evidence-based treatments differ significantly in their proposed pathophysiological basis, mode of administration, acceptance by patients and providers, and availability. These treatments also differ in what is required from the participants. SNS and INJ are treatments provided by the physician and require no effort from the participant; however, BIO requires the participant to learn new skills and requires consistent practice over several weeks, resulting in a greater burden.

Discontinuation rates are greater for BIO than for SNS or INJ. These treatments also appear to differ in safety and cost (Table 1). However, comparisons between treatments are difficult because, with only one exception (see Section 2.2.1), there are no head-to-head comparisons between these treatments. Inconsistencies between existing studies in design, inclusion criteria, and primary endpoints have hampered comparisons between treatment types and even between studies within the same treatment modality. Consequently, meta-analyses and systematic reviews for behavioral treatments, anti-diarrheal medications, BIO, mucosal electrical stimulation, SNS, and INJ have been inconclusive.

Currently, SNS is often regarded as more effective than BIO, although it is associated with a greater risk of side-effects, and a widely accepted clinical algorithm requires patients with FI to have tried and failed conservative treatments before they can be considered candidates for SNS. BIO is usually categorized as one of the conservative treatments which should be tried first.

It could be argued that, even if BIO were to be equally effective as INJ of dextranomer, it would be logical to try BIO first because it is safer, and to only use INJ in those who fail BIO. In practice, however, there is no consistent standard for defining BIO or judging what "failing biofeedback" means. If the proposed comparative effectiveness study shows that BIO is equally effective or more effective than INJ, treatment algorithms and insurance reimbursement policies may need to be re-evaluated. An outcome such as this might also stimulate research into whether treatment combinations may be more consistently effective than trying these treatments one at a time.

An NIDDK Workshop hosted in 2014 addressed research priorities for FI and concluded that the highest priority for research should be "trials comparing the effectiveness, safety, and cost of current therapies". Such a comparative effectiveness study needs to be performed at multiple sites because (1) the number of patients currently referred for these treatments is relatively small at individual medical centers, (2) FI is a multi-faceted disorder and patient phenotypes may differ among centers, and (3) the success of BIO varies across clinical settings and is known to be influenced by the training and experience of the therapist.

Outcome Domain	BIO	INJ	SNS	
Efficacy (success rated by authors' definition)	55%  - 93% 	53% 	83% 	
Efficacy (>75% decrease in FI frequency)	78% 	32% 	56% 	
Continence (%)	5%  - 44% 	5.9% 	25%  - 40% 	
Adverse events (pain or infection)	0% 	10% 	6%  -11% 	
Reimbursement (range in US \$)	\$1,235 – 2,300	\$3,000 - 7,408	\$29,000 - 69,000	

